#### Rationale for Stage 1 Doses

The selection of LY500307 25 mg/day dose for assessment in Stage 1 was based on the extensive preclinical, Phase 1 and Phase 2 BPH trial data sets. This dose was safe, well tolerated and selective for ER $\beta$  receptors without engagement of ER $\alpha$  receptors as demonstrated by the lack of effects on total testosterone levels (Table 3). The 75 mg/day dose was selected based on the Phase 1a multiple dose escalating study (MDES) that demonstrated 100 mg/day was safe, well tolerated and failed to affect

Version: 05.01.17 (Amendment L) Page 12 of 36 plasma testosterone levels. Safety including potential changes in testosterone levels was carefully monitored throughout the trial. If testosterone levels dropped below the normal lower limit of 300 ng/dL, a repeat value was assessed. If the retest value was also below 300 ng/dL, the subject met discontinuation criteria.

#### Rationale for Stage 2 Doses

The rationale for selecting 150 mg/day as the higher dose option is based on data from Lilly's Phase 1 14day multi-dose escalating study (MDES) of LY500307 in healthy male volunteers. This study revealed that no dose, including the highest dose tested at 100 mg/day, suppressed testosterone or was associated with concerning adverse events. Lilly's Phase 1single dosing studies (BPAC and BPAF) reveal no AEs deemed to be "possibly/probably related" to LY500307 at 125 mg/day or 250 mg/day and only one AE (headache) at 500 mg/day (see Table 1 above). In addition to enhancing target engagement in the current Phase 1b/2a study, the 150 mg/day dose will allow for robust dose-concentration-response analyses of biomarker and efficacy endpoints across all arms tested (i.e., placebo, 25 mg/day, 75 mg/day, and 150 mg/day) (see Section 16 below).

#### Addressing Safety in Stage 2

Escalating doses of selective ER $\beta$  agonists have the potential for losing ER $\beta$  selectivity and commence the engagement of ER $\alpha$  receptors which may produce "estrogen-like" effects including adverse events associated with estrogen therapy. One such event is potential thromboembolic events (e.g., deep vein thrombosis, stroke, cardiovascular events). However, the overall rate of thromboembolic events associated with estrogen therapy is relatively low and risk factors for these events include past history of thromboembolic events, advanced age, greater duration of exposure and higher dose estrogen preparations (35, 38-41). We anticipate the risk to be somewhat reduced based on our study sample; the study sample is predominately young-to-middle aged (Stage 1 mean age of 33.9 years old) whereas advanced age is a risk factor for thromboembolic events during estrogen therapy.

A comprehensive safety plan is included in protocol (see Section 9 below) to ensure the safety of subjects participating in Stage 2 and that the risk for "estrogen-like" adverse events including thromboembolic events is mitigated. It has been demonstrated in Lilly's Single Dose Escalating Study (BPAC) that LY500307 related TT suppression occurs relatively rapidly. Therefore, potential cases of TT suppression in this study will be likely detected at week 1 (Visit 2.5), the first post-randomization TT assessment point. Importantly, this relatively short exposure interval and close monitoring of ER $\alpha$  engagement greatly reduces the possibility of experiencing adverse events, particularly an estrogen-like induced thromboembolic event. Moreover, related to the risk that higher dose estrogen preparations have greater thrombogenic potential than lower doses, this risk factor is addressed in the current protocol by purposely dosing LY500307 to avoid ER $\alpha$  receptor binding and thus negating the effects of full estrogen-like receptor activation that occurs with high dose estrogen preparations. In addition, ER $\alpha$  engagement is closely monitored with serial TT sampling. TT and safety will be assessed at screening, baseline, and weeks 1, 2, 4 and 8 during the treatment phase of the study.

#### Rationale for Primary Endpoints

Primary Aim 1: fMRI/N-back was selected as the primary biomarker of cortical target engagement because it has been shown to be sensitive to estrogen (11) and numerous studies have consistently demonstrated that this paradigm demonstrates abnormal frontal and parietal activation in schizophrenia.(42-45)

Primary Aim 2: The Negative Symptom Assessment Scale – 16-item (NSA-16) is a commonly used, validated instrument for assessing negative symptoms in schizophrenia clinical trials (46). The three cognitive tests were chosen because 1) the literature indicates they are sensitive to estrogen (5), 2) they reflect core cognitive impairment in schizophrenia (47) and 3) they are contained in the Measurement and Treatment Research to Improve Cognition in Schizophrenia (MATRICS) Consensus Cognitive Battery (MCCB) which has been validated for schizophrenia treatment trials and endorsed by NIMH and FDA for studies of cognitive impairment associated with this illness (48). The Hopkins Verbal Learning Test has 6 alternative forms to mitigate practice effects and the Letter Number Sequencing and Spatial Span tests have minimal practice effects after the first follow up testing session.

Primary Aim 3: Both estrogen therapy and ER $\alpha$  agonists, but not selective ER $\beta$  agonists, robustly suppress plasma testosterone levels (35, 36). Thus, decreases in plasma testosterone concentrations from baseline levels in the LY500307 arms would reflect ER $\alpha$  engagement. Although schizophrenia and antipsychotic drugs are not directly associated with altered testosterone levels (49), antipsychotics may increase plasma prolactin levels which could secondarily reduce plasma testosterone levels (50). In addition, other factors such as smoking status, age and obesity may influence testosterone concentrations (51). Thus each subject will be used as his own control in assessing LY500307 potential effects on this hormone to address the effects of potential confounds.

NIMH Research Domain Criteria (RDoC) Initiative: The NIMH RDoC initiative, which is a component of the NIMH strategic plan, encourages the assessment of dimensions of observable behaviors and brain functions that may cut across traditional diagnostic categories (see NIMH/RDoC web page). RDoC principles have informed multiple aspects of the study design. While the DSM diagnosis of schizophrenia will be used for entry into the protocol, this heterogeneous disorder will also be characterized by dimensional measures of symptoms, cognitive processes and neurobiological function. This will enable the evaluation in secondary analyses whether these dimensional measures predict treatment response. Second, working memory and episodic memory outcomes will be evaluated across units of analysis, including behavioral, fMRI and ERPs. Three working memory paradigms recommended by the RDoC Working Memory Workshop were selected: N-back (which is coupled with fMRI), Letter Number Sequencing and Spatial Span. The ERP paradigms, P300 and MMN, both exemplify the construct of "Change Detection Tasks." Thus, the findings from this study will likely assist in the validation of the sensitivity of several key RDoC constructs to estrogen modulation across multiple levels of analysis.

### Clinical Research Site

The **IU Psychotic Disorders Program (IUPDP)**, which is directed by the PI ([name]) and part of the IU Department of Psychiatry, is located in Indianapolis, Indiana. IUPDP research personnel will manage the day-to-day activities of conducting the trial, including subject recruitment, consenting and screening subjects, conducting study visits, performing assessments, and study medication management. The IUPDP has three research psychiatrists, a fully dedicated study coordinator, two fully dedicated clinical research specialists, two fully dedicated subject recruiters, three fully dedicated research technicians, a data manager and three raters (1 PhD, 2 Masters level) who have been trained and have extensive experience in conducting the assessments in this application including the NSA-16 (46) and the cognitive tests used as primary outcome measures.

### Sample Size Determination

Thirty subjects will be randomly assigned to three arms (1:1:1) in Stage 1. In Stage 2, 70 additional subjects will be randomized to placebo, the selected LY500307 arm from Stage 1, or the 150 mg/day arm. Thus a total of 100 subjects will be randomized for the study. In a study of chronic schizophrenia,

Version: 05.01.17 (Amendment L) Page 14 of 36 Shekhar et al (52) reported significant effects of the mixed M1/M4 agonist xanomeline (N=20) on verbal and working memory (p < 0.05) and trend effects of negative symptoms (p = 0.08) with effect sizes up to 0.9(52). Based on the estimates from a cross-over study of a nicotinic agonist in patients with schizophrenia (53), it is reasonable to expect an improvement in the working memory score with a mean of 4.5 and a standard deviation of 7.3 using data from the less effective of two doses in that study. Thus for this study, we assume a treatment effect size of 0.61 between the placebo group and the LY500307 treated group. The power estimate based on the variance of the change is conservative for the proposed analyses that actually use baseline outcome values as covariates. We will test the treatment effects on the three primary efficacy measures (negative symptoms, working memory and verbal episodic memory) at the end of Stage 2 with one-tailed tests at an overall alpha=0.1 (see Stage 2 Efficacy Analysis in Section 16.0). Adjusting for multiple comparisons, the test for each of the three individual efficacy outcomes will be performed at alpha=0.0333. The fMRI data will be tested at alpha=0.05. With 30 subjects each in the placebo, 75mg and 150 mg groups across the entire study, 10 subjects assigned to 25 mg/day from Stage 1, and the employment of the dose-concentration-response analytic strategy, we will have >80% power to detect a beneficial treatment effect on each outcome for any effect size >0.61 (measured in SD of the change).

# 5. Study Population (Inclusion/Exclusion Criteria)

Medically stable male subjects with a confirmed diagnosis of schizophrenia as determined by the Structured Clinical Interview for DSM-IV-TR (SCID) (54) interview will be enrolled in the trial. The rationale for including only males is based on the lack of data on females in the Lilly LY500307 Phase 1 and 2 data sets. If the results of the current proposal are positive, Phase 1 studies in females with schizophrenia could be rapidly conducted and females could then be potentially included in future Phase 2 and 3 trials.

Clinical trial guidelines established by the NIMH sponsored MATRICS initiative (55) was used for the proposed trial. As recommended by MATRICS, subjects will meet DSM IV-TR diagnostic criteria for schizophrenia and will be clinically stable prior to enrollment. Enrolling stable subjects will help to isolate changes in cognitive and negative symptoms apart from changes in other symptoms and clinical features. Extrapyramidal signs may confound interpretation of therapeutic effects on cognition and negative symptoms so only subjects without significant EPS will be enrolled. Treatments with anticholinergic properties will be monitored throughout the trial using the Anticholinergic Cognitive Burden Scale (ABS) (56). Guidelines developed for assessing the efficacy of agents for cognitive impairment associated with schizophrenia do not recommend excluding patients based on their cholinergic medication scores. The 1:1:1.5 randomization used in this study will mitigate the preferential effects of medication properties on the experimental arm. Analyses are based on change from baseline cognitive testing which will mitigate preferential effects of medication properties on the experimental arm. Previously reported studies demonstrating positive effects of agents on cognition in schizophrenia did not screen out patients based on ABS scores. Therefore, the ABS will be used to monitor psychotropic medications based on their anticholinergic effects and not used to determine inclusion/exclusion. MATRICS recommends adding the investigational compound to a stable regimen of antipsychotic drug therapy to further minimize the likelihood that changes in psychosis and other clinical features of schizophrenia during the study will compromise the interpretation of primary drug effects on cognition. The MATRICS guidelines do not recommend requiring minimum cut off scores on cognitive tests as inclusion criteria. However, a minimum level of negative symptoms will be required for inclusion in the current study.

### Inclusion Criteria:

Version: 05.01.17 (Amendment L) Page 15 of 36

- 1. 18 to 65 years of age at study entry
- 2. Male
- 3. DSM IV-TR diagnosis of schizophrenia as confirmed by Structured Clinical Interview for DSM-IV-TR (SCID)
- 4. Outpatient or inpatient status
- 5. Mild to moderate overall disease severity as defined by a CGI-S score of less than or equal to 4 (moderately ill) at randomization
- 6. Moderate levels of negative symptoms as defined by a PANSS negative symptom sub-score  $\geq 11$ .
- 7. Clinical stability as defined by:
  - a. No exacerbation of illness leading to an intensification of treatment in the opinion of the investigator within four weeks prior to randomization

### Exclusion Criteria:

- 1. Subjects with current acute, serious, or unstable medical conditions, including, but not limited to: inadequately controlled diabetes, asthma, COPD, severe hypertriglyceridemia, recent cerebrovascular accidents, acute systemic infection or immunologic disease, unstable cardiovascular disorders, malnutrition, or hepatic, renal gastroenterologic, respiratory, endocrinologic, neurologic, hematologic, or infectious diseases
- 2. Known or suspected history of prostate cancer, breast cancer, or other clinically significant neoplastic disease (other than squamous cell or basal cell carcinoma of skin)
- 3. Known or suspected history of thromboembolic events including deep venous thrombosis, stroke, venous thromboembolism, pulmonary embolism, paresis or paralysis that may be thrombogenic in origin.
- 4. Subjects currently receiving testosterone replacement therapy or drugs that influence the hypothalamus-pituitary-gonadal axis.
- 5. Subjects who have clinically significant extrapyramidal signs (EPS) as defined by a score of >20 on the Simpson-Angus Scale (SAS) (57)
- 6. Clinically significant electrocardiogram (ECG) abnormality, including, but not limited to, a corrected QT interval (Bazett's; QTcB) >450 msec. Repeat ECGs may be conducted at the discretion of the principal investigator.
- 7. Subjects with known medical history of Human Immunodeficiency Virus positive (HIV+) status
- 8. Subjects with an active seizure disorder
- 9. Subjects with implanted pacemaker, medication pump, vagal stimulator, deep brain stimulator, TENS unit, ventriculoperitoneal shunt, or other contraindication to undergoing an MRI scan
- 10. Known IQ less than 70 based on medical history
- 11. Current DSM IV-TR diagnosis of substance dependence (excluding caffeine and nicotine)
- 12. Subjects who test positive for (1) Hepatitis C virus antibody or (2) Hepatitis B surface antigen (HBsAg) with or without positive Hepatitis B core total antibody
- 13. Subjects with moderate to severe renal impairment as defined by creatinine clearance (CrCl) < 60 ml/min (measured by the Cockcroft-Gault equation) at screening. Repeat evaluation may be conducted at the discretion of the Principal Investigator.
- Subjects with hepatic impairment as defined by liver transaminases or total bilirubin > 3 × upper limit of normal (ULN). Repeat evaluation may be conducted at the discretion of the Principal Investigator.
- 15. Subjects considered a high risk for suicidal acts active suicidal ideation as determined by clinical interview OR any suicide attempt in 30 days prior to screening
- 16. Subjects who have participated in a clinical trial with any pharmacological treatment intervention for which they received study-related medication in the four weeks prior to randomization OR subjects currently receiving treatment (within 1 dosing interval plus four weeks) with an investigational depot formulation of an antipsychotic medication
- 17. Subjects who demonstrate overtly aggressive behavior or who are deemed to pose a substantial risk of danger in the Investigator's opinion

Version: 05.01.17 (Amendment L) Page 16 of 36

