# 8. Clinical Assessments and Procedures

### Primary Efficacy Outcome Measures:

Negative Symptom Assessment Scale – 16-item (NSA-16), a primary outcome measure, is used to help clinicians rate behaviors (not psychopathology) commonly associated with negative symptoms of schizophrenia. The scale rates subjects on 16 "anchors," is a semi-structured, clinical interview, and each item is rated from 1 to 6. The total score is the sum of the 16 specific items and ranges from 16 to 96; a higher score indicates greater severity of illness. In addition, there is a global rating which represents the overall assessment of a subject's negative symptoms. The rating should not be an average of any particular behavior, but a gestalt of everything observed in the interview (58).

Hopkins Verbal Learning Test-Revised, Wechsler Memory Scale-Third Ed, Spatial Span, and Letter-Number Sequencing are cognitive tests for verbal memory (Hopkins) and working memory (Spatial Span and Letter-Number Sequencing combined as a single composite score). These tests are part of the MCCB (48) which has proven reliability for clinical trials of cognitive impairment associated with schizophrenia. For each cognitive test, a multi-item score will be derived based on the raw item values according to the MCCB scoring manual. Each of the individual item raw scores is standardized to ageand gender-corrected t-scores (mean=50, standard deviation=10). Each working memory test will be converted in to a single domain score.

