Clinical Global Impression Change Scale (CGI-I) (59) is used to assess the clinical change as compared to symptoms at baseline using a 7-point Likert scale, ranging from very much improved (1) to very much worse (7).

The Positive and Negative Syndrome Scale (PANSS) (60) is an assessment instrument for general psychopathology and positive symptoms. The PANSS contains 30 items that assess symptoms of psychotic disorders including positive, negative and general psychopathology. The PANSS was chosen because of its widespread use in clinical studies of psychosis, and its demonstrated reliability in assessing psychopathology across diverse patient populations.

Personal and Social Performance Scale (PSP) (61) is a 100-point, single item, clinician rated scale to assess 4 domains of functioning, including personal and social relationships, socially useful activities, self-care and disturbing and aggressive behaviors.

**Quality of Life Scale (QLS)** (62) assesses multiple dimensions of quality of life. It was developed specifically for schizophrenia populations and is commonly employed in clinical trials.

**Barnes Akathisia Scale (BARS)** (63) is used to rate drug-induced akathisia. Symptoms are rated on a 4-point scale, with 0 being no akathisia and 3 being severe akathisia. A global clinical assessment of akathisia is then scored on a 6-point scale, with 0 being no evidence of akathisia and 5 being severe akathisia.

Simpson Angus Scale (SAS) (57) is a 10-item scale used to evaluate the presence and severity of drug induced Parkinsonism. Each item is rated from 0 to 4.

Calgary Depression Scale for Schizophrenia (CDSS) (64) is a nine-itemed structured interview specifically developed for assessment of depression in patients with schizophrenia. Items are scored from 0 (absent) to 3 (severe).

Columbia Suicide Severity Rating Scale (C-SSRS) (65) captures the occurrence, severity, and frequency of suicide-related thoughts and behaviors during the assessment period. The definition of behavioral suicidal events used in this scale is based on those used in the Columbia Suicide History Form (66). During the baseline assessment, questions are in relation to lifetime experiences and all subsequent questioning is in relation to the last assessment.

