Covariates in Regression Models: The baseline value of the outcome, centered about its sample mean, will be included in each analysis. The baseline value tends to correlate with post-randomization

Version: 05.01.17 (Amendment L) Page 26 of 36 outcomes, and this maneuver reduces residual variance, thus increasing statistical power and the precision of the estimated treatment effect. Otherwise, only a small number of prognostic factors, e.g. age, found to be imbalanced at baseline, will also be entered into the model.

Missing Data: For this study, missing data falls in to one of two general categories: The first is data that is missing because of missed visits or early termination. The second is related to incomplete data. The former will not affect the results of the mixed-effects model, which is unbiased if missing-at-random assumptions are met; sensitivity analyses will also be performed as described below. The problem of incomplete data in composite measures will be addressed in the case of the cognitive measures by following MATRICS Neurocognition Committee guidelines for imputation (94). For other instruments, total and subscale scores will be imputed using the average of the available items as long as 80% or more of the individual items are available. A low dropout rate is anticipated because subjects will have met a priori clinical stability criteria before randomization and those agents will not be altered throughout the course of the active treatment phase. For drop-outs, sensitivity analyses will as multiple imputations if drop-out is higher than expected.

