Other Confounders Arising Post-Randomization: Analyses will be conducted to investigate: (a) adherence to the assigned study medication, (b) co-administration of psychotropic medications, and (c) discontinuation from the study intervention, and logistic regression analysis will be applied to investigate these factors. First, it will determine whether these effects occur differentially across the treatment arms suggesting that a differential selection bias may have influenced the results. Then, whether baseline characteristics are predictive of any behavior will be evaluated. This will include demographic characteristics, initial severity as measured by the baseline values of the outcome variables, and clinical characteristics such as diagnoses and medications taken at baseline. Finally, these confounding factors will be included as covariates in the primary analyses to investigate whether the conclusions on treatment effects are altered.

Pharmacokinetics (PK): These data will be used in post hoc analyses to potentially explain inter-subject variability and toxicity.

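### The SAS exclusion admits men with up to half-maximal extrapyramidal signs, and no efficacy model is committed to adjusting for baseline SAS

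*Combined protocol and SAP*

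**What the plan says.** Section 5 gives the purpose: "Extrapyramidal signs may confound interpretation of therapeutic effects on cognition and negative symptoms so only subjects without significant EPS will be enrolled". Exclusion Criterion 5 puts this into practice by barring men with "clinically significant extrapyramidal signs (EPS) as defined by a score of >20 on the Simpson-Angus Scale (SAS"). Section 8, under Secondary Outcome Measures, says the SAS "is a 10-item scale used to evaluate the presence and severity of drug induced Parkinsonism. Each item is rated from 0 to 4". No section gives a reason for the value 20.

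Attachment A schedules the SAS at Visits 1, 2, 4 and 6. Its place among the secondary outcomes matters, because the Repeated Measures paragraph of Section 16 applies the mixed model to every primary and secondary outcome. SAS will therefore be compared by arm.

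For the efficacy models, Section 16 (Covariates in Regression Models) states: "The baseline value of the outcome, centered about its sample mean, will be included in each analysis". Beyond that, "only a small number of prognostic factors, e.g. age, found to be imbalanced at baseline, will also be entered into the model". The paragraph on confounders arising after randomization names three: "a) adherence to the assigned study medication, (b) co-administration of psychotropic medications, and (c) discontinuation from the study intervention". EPS is not among them.

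**The concern.** The aim and the threshold fit poorly. The protocol names EPS as a threat to two of its efficacy domains, then sets a limit that leaves the lower half of the scale eligible. The NSA-16 "is used to help clinicians rate behaviors (not psychopathology) commonly associated with negative symptoms of schizophrenia", so some overlap between a parkinsonian sign and a rated negative symptom is plausible, although the documents do not quantify it.

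At stake is the clarity of a small efficacy signal. EPS that is stable over eight weeks adds between-subject variation to the endpoint. EPS that is unevenly spread at baseline, or that moves differently by arm, could shift the treatment contrast. One route for movement is background medication. Section 16 (Missing Data) expects background agents to stay unaltered, but Attachment B allows antipsychotics without the stable-dose note it attaches to several other drug classes.

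The plan measures SAS before the first dose but makes its use in the efficacy models depend on an observed imbalance. A covariate chosen after looking at baseline tables is weaker than one fixed in advance, and it gives up the precision gain whenever the arms happen to be balanced.

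**Working it through.** **Scale arithmetic** (inputs: Exclusion Criterion 5; Section 8)

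- Maximum total: 10 items × 4 = 40.
- Highest eligible total: 20, and 20/40 = 50% of the maximum.
- Mean item rating at that total: 20/10 = 2.0. A man with all ten items at 2, or five items at 4 and five at 0 (5 × 4 = 20), is eligible.
- Eligible totals are 0 to 20, which is 21 of 41 possible values. Totals 21 to 40 are excluded.

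**The plan's own power figure** (inputs: Sample Size Determination)

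The cited improvement gives 4.5/7.3 = 0.616, which the plan takes as 0.61. On significance level, "the test for each of the three individual efficacy outcomes will be performed at alpha=0.0333", one-sided. For a two-group comparison, power comes from the noncentral t distribution with λ = d × √(n₁n₂/(n₁+n₂)).

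- 30 placebo against 70 pooled active: λ = 0.61 × √(2100/100) = 0.61 × 4.583 = 2.795; critical t (98 df) = 1.855; power 82.6%.
- 30 against 30 (one dose): λ = 0.61 × √(900/60) = 0.61 × 3.873 = 2.362; critical t (58 df) = 1.870; power 68.9%.

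The plan's figure of more than 80% is therefore reproduced with active arms pooled, but not for a single dose. A normal approximation gives 83.2% and 70.1%; the difference does not affect this point.

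**Gain from a baseline SAS covariate**

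Let R² be the share of the residual NSA-16 variance that Visit 2 SAS explains. The documents give no value, so 3% to 10% is an assumption. The effective effect size is d = 0.61/√(1 − R²).

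| R² (assumed) | d | 30 v 70 | 30 v 30 |
|---|---|---|---|
| 0 | 0.610 | 82.6% | 68.9% |
| 0.03 | 0.619 | 83.6% | 70.2% |
| 0.10 | 0.643 | 86.1% | 73.2% |

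The gain is about 1 to 4 percentage points. Spending one degree of freedom on the covariate (97 instead of 98, or 57 instead of 58) changes these results by less than 0.1 point.

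The calculation is a two-group approximation. It does not represent the concentration-response model, which is the primary approach if 150 mg/day is kept. It also measures the value of the covariate at any cut-off, not the loss caused by this cut-off. That loss cannot be computed, because the documents do not say how many men score near 20.

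**The case against.** The strongest reply is that the plan does not contradict itself. Section 5 promises men without significant EPS, and Exclusion Criterion 5 defines what significant means. Section 5 says only that EPS may confound. Calling 20 too high needs a clinical norm for the SAS, which the documents do not contain, and half a scale's range is not itself a benchmark. This stands, and it is why no replacement cut-off is offered.

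The protections are also better than a first look suggests. Totals above 20 are excluded. Randomization and adjustment for the baseline outcome leave stable EPS mainly as noise. SAS is analysed by arm as a secondary outcome, so a differential shift would be examined. Psychotropic co-medication is to be compared across arms and tried as a covariate. Baseline SAS can enter the model if it is found imbalanced. All of this stands. What remains is that SAS is not committed to any efficacy model and that the cut-off is not justified against its stated purpose.

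Four stronger readings are tempting but unsupported:

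- A reader might infer that the EPS safeguard is absent. It is present but permissive.
- A reader might infer that EPS confounding is built into the endpoints. Bias needs imbalance or differential change, and neither is shown.
- A reader might suppose the score could be recorded as an item mean, so that the rule could never bite. Nothing suggests that; an item mean cannot exceed 4, so a limit of 20 evidently refers to the sum.
- A reader might conclude that EPS takes power below 80%. If EPS made up 10% of the variance on top of the planned SD, d would be 0.61 × √0.90 = 0.579 and 30 v 70 power 78.7%. The documents support neither the 10% nor its being additional.

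**Conclusion.** The point holds as a mismatch between purpose and threshold, together with an avoidable gap in the analysis plan. Men with SAS totals up to 20 of 40 are eligible, no reason is given for that limit, and baseline SAS reaches the NSA-16 and cognition models only through the imbalance rule.

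The consequence is possible noise, and bias only under imbalance or differential change. The measurable benefit of the remedy is small: about 1 to 4 points of power, resting on an assumed 3% to 10% of residual variance, a 0.61 SD effect and a two-group approximation. It matters most if the trial ends with a small or ambiguous negative-symptom signal, when the question of whether EPS explains it will be asked anyway. This is a low-cost improvement, not a flaw that invalidates the design.

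**What to change.** In Section 16:

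1. Pre-specify the Visit 2 SAS total, stated to be the item sum, as a fixed covariate in the NSA-16 model, whether or not it is imbalanced.
2. Pre-specify a sensitivity analysis that adds the same covariate to the working-memory and verbal-memory models.
3. State that SAS change by arm, already analysed as a secondary outcome, will be interpreted beside these endpoints. SAS measured after baseline should not become a covariate in the primary model, because treatment could affect it.

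The cost is a few lines of text and one model degree of freedom, with no new assessments.

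Separately, the investigators should reconcile the purpose in Section 5, the limit in Exclusion Criterion 5 and the scale in Section 8 by justifying the cut-off or revisiting it. Any change now has a price. Stage 1 is pooled with Stage 2, the 25 mg/day arm exists only in Stage 1 and the 150 mg/day arm only in Stage 2. A new entry limit would thus be partly aligned with dose in an analysis built on dose and exposure, and that should be weighed before eligibility is altered.
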